4.17.2 Intraocular Pressure

Intraocular pressure and change from baseline will be summarised by visit, by eye, by period as well as overall.

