5.4 Risk / Benefit Assessment

No treatment currently exists for CHM.

The non-clinical studies conducted with AAV2-REP1 showed that it provides efficient and functional transgene expression in CHM mouse and human cells, as well as in mouse and human RPE and photoreceptors, without overt toxicity. Results from the 26-week single-dose combined toxicity/biodistribution study conducted in rats indicate that administration of AAV2-REP1 by single sub-retinal injection to both eyes is well tolerated at dose levels of 1×10^9 and 6×10^9 gp/eye (equal to 1×10^{11} and 6×10^{11} gp/eye in humans) when evaluated 4 and 26 weeks after injection. Minor reductions in some ERG parameters, ocular inflammation, and microscopic signs of retinal/corneal degeneration were observed and were considered procedure-related or not biologically significant.

In humans, application of AAV2-REP1 to the surface of the retina requires retinal detachment via vitrectomy. The 2-step procedure employed in delivering AAV2-REP1 sub-retinally (see [Section 9.4](#)), allows the management of unexpected surgical complications of retinal detachment before the AAV2-REP1 is applied. Furthermore, since the volume of fluid required to detach the fovea is variable, by excluding the vector from the first step, and administering the vector after successful retinal detachment has been achieved, a precise, consistent dose in terms of genome particles can be applied into the sub-retinal space.

Nevertheless, sub-retinal injection of AAV2-REP1 carries the risks associated with vitrectomy and retinal detachment, which include intra-operative and post-operative complications; infection (most notably infectious endophthalmitis); low and elevated IOP; choroidal detachment; persistent retinal detachment, retinal tears, holes and breaks; macular hole and macular oedema; vitreous haemorrhage; visual impairment; metamorphopsia; and photopsia ([Park, Marcus et al. 1995](#), [Thompson, Sjaarda et al. 1996](#), [Banker, Freeman et al.](#)

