10.10 Unscheduled Visits

If clinically indicated, subjects may need to return to the site for an unscheduled visit. At a minimum, the following assessments will be performed (ophthalmic assessments will be conducted on any eye deemed appropriate by the Investigator):

- BCVA
- Full ophthalmic examination, including IOP, a slit-lamp examination, lens opacity, and dilated fundus examination
- SD-OCT
- AE/SAE monitoring
- Concomitant medication, procedures and treatment review (including review / return of the corticosteroid diary card, if applicable)

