11 ASSESSMENT OF SAFETY

11.1 Evaluation, Recording, and Reporting Adverse Events

11.1.1 Definitions

11.1.1.1 Adverse Event

An AE is any untoward medical occurrence in a clinical investigation subject, which does not necessarily have a causal relationship with the study drug/surgical procedure. An AE can therefore be any unfavourable and unintended sign (including an abnormal laboratory finding), symptom, or disease temporally associated with the use of the study drug/surgical procedure, whether or not related to the investigational product or with the surgical procedure described in this protocol.

AEs are to also include any pre-existing condition (other than CHM) or illness that worsens during the study (i.e., increases in frequency or intensity).

Worsening of the signs, symptoms and visual function related to CHM is not to be considered an AE unless, in the opinion of the Investigator, the changes are not consistent with the natural progression of the disease.

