13.6.2 Ophthalmic Examination

IOP and change from Baseline in IOP will be summarised by eye, period and visit. Abnormal slit lamp examination findings and dilated ophthalmoscopy findings will be summarised by eye, period and visit. Lens opacity categories and shifts from baseline will be summarised by eye, period and visit.

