4.2 Conventions

Summary statistics will be presented for continuous variables, by way of number of subjects, mean, standard deviation (SD), median, first and third quartiles (Q1 and Q3, respectively), 5th and 95th percentiles (P05 and P95, respectively), minimum and maximum. For categorical variables including binary variables, counts and percentages will be presented. Percentages will be calculated using the total number of eyes in the respective column or the total number of eyes with an assessment, the total number of treated subjects, depending on the nature of the analysis.

In addition, 95% 2-sided confidence intervals (CIs) will be presented, where specified. The 95% CI of the mean value of an assessment will be calculated using the t-test formula. The 95% CI of the mean of change from baseline of an assessment will be calculated using the t-test formula. In case of percentages, the CI will be computed using the Clopper-Pearson method. (See [Section 4.21](#) for the corresponding SAS code).

No formal statistical comparison will be performed.

Summary statistics will be presented by period and overall for all endpoints. For selected endpoints (see details below), summary statistics will also be presented by Surgery Window (Short [<6 months], Medium [6-12 months] and Long [>12 months]) and overall. Where appropriate, summary statistics will be displayed by eye (SE1 and SE2), and by period.

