4.16.1 Visual Acuity

Best-corrected visual acuity (BCVA) and change from baseline will be summarised by visit, by eye, by period as well as overall. The corresponding 95% CIs will be calculated (See [Section 4.2](#)).

Furthermore, the proportion of eyes with a ≥ 10 letters increase, a ≥ 15 letters increase, and an increase or a loss < 5 letters (i.e. change from baseline > -5 letters) will be summarised by visit, by eye, by period as well as overall. The corresponding 95% CI will be presented (See [Section 4.2](#)).

The above main analyses will use the observed case method only. Imputation using LOCF method regardless of the reasons of missing data will be performed for supportive analyses (See [Section 4.8](#)).

In addition to the by-period, by-eye presentation mentioned above, as supportive analyses, for both continuous and categorical endpoints, the period 2 Study Eye 1 data will be presented by

remapping them to visits after their last visit in period 1 and calculating change from baseline using baseline at period 1 for the same eye (Study Eye 1). This way a full picture of Study Eye 1 treatment journey during the entire study will be presented.

For all assessments of periods 1 and 2 of Study Eye 1, the data records will be assigned to calculated visit window (using study day) as described in [Table 2](#) below. The window of the visits following baseline (including unscheduled visits) will be constructed in such a way that the upper limit of the interval falls half way between the two visits.

If a patient has more than one assessment included within a window, the assessment closest to the target day will be used. In case of ties between observations located on different sides of the target date, the value with the later date will be used.

Table 2 **Visit Assignment Windows**

Day / Month	Target Day	Day Range included in the visit
Baseline	0	The last assessment on or before day 0
Day 1	1	Day 1
Day 3	3	Day 2 to 5
Day 7	7	Day 6 to 10
Day 14	14	Day 11 to 22
Month 1	30	Day 23 to 61
Month 3	91	Day 62 to 136
Month 6	182	Day 137 to 272
Month 9	273	Day 228 to 318
Month 12	365	Day 319 to 410
Month 15	456	Day 411 to 501
Month 18	548	Day 502 to 593
Month 21	639	Day 594 to 684
Month 24	731	Day 685 onwards

Both continuous and categorical endpoints for BCVA will be summarised by subgroups mentioned in [Section 4.7](#).

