4.17.10 Adverse Events

Treatment Emergent Adverse Events (TEAEs) are defined as AEs starting on or after the day of the first surgery. AEs reported in subjects who received timrepigene emparvovec treatment in their first eye in an antecedent study will be considered as TEAEs. Where an AE start date is partially or fully missing, and it is unclear as to whether the AE is treatment emergent, it will be assumed that it is. Summary tables will include TEAEs only. TEAEs will be summarised by eye (for ocular events), by period, and overall. Each by-period summary table will be repeated by surgery window instead.

The number and percentage of subjects reporting any event, any non-ocular event, any ocular event, any ocular event in SE1 and any ocular event in SE2 will be summarised. Percentage will be calculated based on the number of subjects in the corresponding period or surgery window or overall. The 95% CI will be calculated using the Clopper-Pearson method.

Overall summary table of TEAE by period (or by surgery window) will be provided for the following categories:

- Number and percentage of subjects with a TEAE
- Number and percentage of subjects with a serious TEAE
- Number and percentage of subjects with a Treatment-related (study drug or study procedure) TEAE
- Number and percentage of subjects with a Treatment-related (study drug or study procedure) serious TEAE
- Number and percentage of subjects with a TEAE leading to death
- Number and percentage of subjects who discontinued due to a TEAE
- Number and percentage of subjects with a TEAE by severity
- Number and percentage of subjects with a TEAE by outcome
- Number and percentage of subjects with a TEAE by action taken

Adverse events will be summarized by period (or by surgery window), and overall. The following summaries of TEAEs will be provided:

- TEAEs by SOC and PT
- TEAEs by PT with percentage $\geq 5\%$
- Treatment-related (study drug or study procedure) TEAEs by SOC and PT
- Study procedure-related TEAEs by SOC and PT
- Study drug-related TEAEs by SOC and PT
- TEAEs by SOC, PT, and maximum severity (missing severity, if any, will be counted as severe).
- Serious TEAEs by SOC and PT
- Treatment-related (study drug or study procedure) serious TEAEs by SOC and PT
- Study procedure-related serious TEAEs by SOC and PT
- Study drug-related serious TEAEs by SOC and PT
- TEAEs leading to death by SOC and PT
- TEAEs reported by subjects who discontinued due to SAE by SOC and PT

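### Low and elevated IOP are named surgical risks, but the SAP plans no count of eyes with a measured high or low pressure

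*SAP*

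**What the plan says.** Protocol 5.4 includes among the risks of vitrectomy and retinal detachment "low and elevated IOP; choroidal detachment; persistent retinal detachment". IOP belongs to the ophthalmic examination listed among the safety measures (protocol 6.2, SAP 2.2.1). It is measured at screening, at Period 2 baseline and at all scheduled visits from Visit 1 to Visit 9 (protocol Table 1). Unscheduled visits also require it, on whichever eye the investigator thinks appropriate: "Full ophthalmic examination, including IOP, a slit-lamp examination, lens opacity, and dilated fundus examination" (protocol 10.10).

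The planned analysis in SAP 4.17.2 is "Intraocular pressure and change from baseline will be summarised by visit, by eye, by period as well as overall". Protocol 13.6.2 is equivalent: "IOP and change from Baseline in IOP will be summarised by eye, period and visit". SAP 4.2 sets the statistics for a continuous variable, which include quartiles and "5th and 95th percentiles (P05 and P95, respectively), minimum and maximum". It gives confidence intervals only where a section asks for them, and 4.17.2 does not ask.

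Adverse events follow a separate route. The definition in protocol 11.1.1.1 covers "any unfavourable and unintended sign (including an abnormal laboratory finding), symptom, or disease temporally associated", which can include a pressure finding. SAP 4.17.10 states: "TEAEs will be summarised by eye (for ocular events), by period, and overall. Each by-period summary table will be repeated by surgery window instead".

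**The concern.** For a pressure risk in a study whose sole objective is safety, the informative result is how many eyes went too high or too low, and whether this happened at any time after surgery. A by-visit continuous summary does not answer either question. Neighbouring SAP sections do give counts: visual acuity has three loss thresholds with intervals (4.17.1), and slit lamp, lens opacity and ophthalmoscopy have category counts and shifts (4.17.3 to 4.17.5). IOP has no limit, category, shift table or worst post-surgery value.

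The adverse-event tables fill part of the gap, but neither document gives a pressure value at which an event must be reported. The explicit rule for measured values in protocol 11.1.2 concerns laboratory results and vital signs, and vital signs are pulse and blood pressure (protocol 11.5). The planned IOP event count therefore rests on each investigator's own reporting threshold. SAP 4.17.2 also does not say how unscheduled readings enter.

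**Working it through.** The plan states no figure for IOP, so there is none to reproduce. The check has two parts.

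**1. Which planned outputs count eyes with abnormal pressure?**
- SAP 4.17.2: none. It gives value and change only.
- SAP 4.17.10: yes, for pressure events reported as adverse events.
- SAP 4.14: partly. Ocular medications are tabulated by class, preferred term, eye and period, so treated pressure shows there. Prophylactic use would be mixed in.
- Source listings (SAP 5.2): individual values can be looked up, but nothing is counted.
- Unscheduled readings: the only windowing rule that mentions them is in the visual acuity section (SAP 4.16.1), for Study Eye 1. There, "If a patient has more than one assessment included within a window, the assessment closest to the target day will be used". It does not govern IOP.

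What remains uncounted is measured high or low readings that were neither reported as events nor treated with ocular medication.

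**2. Can the count be recovered from the displayed percentiles and extremes?**

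Inputs:
- First eyes treated in this study: 60 planned − 6 treated in an antecedent study (SAP 4.4) = 54.
- Second eyes: 60, if every planned subject has the second surgery.
- Assumptions: no missing readings, and the default percentile definition of SAS PROC UNIVARIATE, since SAP 4.21 sets no other. Under that definition, if n × p is not a whole number, the percentile is the next ordered value. If it is a whole number j, the percentile is the mean of the j-th and (j+1)-th ordered values.
- The limit is left unspecified, because the documents give none.

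First eyes, n = 54:
- P95: 54 × 0.95 = 51.3, so the 52nd value. Q3: 54 × 0.75 = 40.5, so the 41st.
- P95 beyond the limit puts values 52 to 54 beyond it, so at least 3 eyes. Q3 within it allows at most 54 − 41 = 13. Range: 3 to 13 eyes (5.6% to 24.1%).
- If P95 is within and only the maximum is beyond, value 52 is within, so 1 or 2 eyes are beyond.
- If that pattern occurs at all five visits from Day 1 to Month 1, the any-visit count runs from 1 (the same eye each time) to 5 × 2 = 10 (different eyes each time), or 1.9% to 18.5%.

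Second eyes, n = 60:
- P95: 60 × 0.95 = 57, so the mean of values 57 and 58. Q3: 60 × 0.75 = 45, so the mean of values 45 and 46.
- P95 beyond requires value 58 to be beyond, so at least 3 eyes. Q3 within requires value 45 to be within, so at most 15. Range: 3 to 15 eyes (5.0% to 25.0%).
- If only the maximum is beyond: 1 to 3 eyes. Over five visits: 1 to 5 × 3 = 15 eyes (1.7% to 25.0%).

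The low side is symmetric, using P05, Q1 and the minimum.

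The tables therefore show that an extreme reading occurred, but not in how many eyes. They also cannot show whether the same eyes recur across visits.

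Precision of the missing count, by the Clopper-Pearson method already in SAP 4.2: 3/54 = 5.6% (95% CI 1.2 to 15.4); 3/60 = 5.0% (1.0 to 13.9).

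**The case against.** The plan does what the protocol specifies. The study is descriptive, with no formal comparison and no sample size calculation, so no error rate is affected. Reported pressure events are counted per eye, treated pressure appears in the medication tables, extremes are displayed at every visit, and values are listed. Serious consequences in the cornea, choroid or optic nerve would enter their own shift tables. What is left is mainly readings that the investigator did not consider adverse, and the documents do not show that these matter clinically. The numerical ranges would be the same for any continuous variable. All of this stands, and it limits the point to a minor one.

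The worry that a limit would be chosen after seeing the data also carries little weight in an open-label, single-arm study without testing. It is still a reason to fix the limits early, because doing so costs nothing.

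A simple any-visit count by period would bring problems of its own. SAP 4.3 resets the baseline of Study Eye 1 at Period 2 to a post-treatment value, so pressure already raised by then would show no rise. Period 1 length varies between subjects. Unscheduled readings are clinically driven. Six first eyes had their surgery outside this study. These objections stand and shape the fix.

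A reader might infer that pressure problems go uncounted altogether, or that extreme values are hidden. The documents do not support that: SAP 4.17.10 and 4.14 provide counts, and SAP 4.2 displays the extremes.

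**Conclusion.** The point holds as a minor one. For a risk named in both directions, the proportion of eyes with a measured high or low pressure, by visit or at any time after surgery, is produced only where an investigator reported an event or treated it with ocular medication. No planned number is wrong or biased.

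The ranges of 3 to 13 of 54 and 3 to 15 of 60 eyes show only that percentiles and extremes do not yield a count. They rest on complete data, the SAS default percentile definition and an unspecified limit. The five-visit ranges also assume the same pattern at every visit, and their upper ends need different eyes each time. A reader might take any of these as an expected number of affected eyes, or as evidence that a safety signal will be missed. Nothing in the documents supports either reading.

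**What to change.** Keep the continuous summary and add one table to SAP 4.17.2:

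- **Counts.** By eye, the number and percentage of eyes, with Clopper-Pearson 95% CI, above a high limit, below a low limit, and with a rise or a fall from baseline beyond a set amount. The sponsor's clinicians fix the limits before database lock.
- **Baseline.** Each eye's last value before its own surgery: the Period 1 baseline for Study Eye 1 and the Period 2 baseline for Study Eye 2. Do not use the reset Period 2 baseline for Study Eye 1.
- **Timing.** At each scheduled visit, and at any visit after that eye's surgery through a common follow-up window, for example to Month 1 and to Month 12. For Study Eye 1, readings taken in Period 2 count by time since its own surgery.
- **Unscheduled readings.** Show the any-visit count with and without them.
- **Antecedent eyes.** Leave the six first eyes treated in an antecedent study out of the any-visit and change-from-baseline counts for Study Eye 1.

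The cost is SAP wording and one table from data already collected, with no patient or site burden. The downsides are fairly wide intervals and an any-visit count that depends partly on how often an eye is measured.

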4.17.3 Slit Lamp Examination

The number and percentage of subjects within each category of Slit Lamp Examinations outcomes will be summarised by visit, by eye, by period as well as overall. Shift from baseline will also be evaluated.

The categories for the shift from baseline for ‘Cornea’, ‘Conjunctiva’, ‘Iris’, ‘Lens’ and ‘Anterior Segment’ assessments are defined as follows:

- Normal/Clinically insignificant abnormality at Baseline to Normal/Clinically insignificant abnormality
- Normal/Clinically insignificant abnormality at Baseline to Clinically significant abnormality
- Clinically significant abnormality at Baseline to Normal/Clinically insignificant abnormality
- Clinically significant abnormality at Baseline to Clinically significant abnormality

The categories for the shift from baseline for ‘Anterior chamber, hypopyon’, ‘Grading of anterior chamber cells’, ‘Grading of anterior chamber flare’ and ‘Vitreous inflammation quantification’ assessments are defined as follows:

- Absent at Baseline to absent
- Absent at Baseline to present
- Present at Baseline to absent
- Present at Baseline to present

For ‘Grading of anterior chamber cells’ assessment, absent is defined as ‘0 Cells’ and present is defined as any other category (except missing).

For 'Grading of anterior chamber flare' assessment, absent is defined as 'Complete absence' and present is defined as any other category (except missing).

For 'Vitreous inflammation quantification' assessment, absent is defined as '0' and present is defined as any other category (except missing).

4.17.4 Lens Opacity Grades

The number and percentage of subjects within each category of Nuclear Opalescence Grade, Nuclear Colour Grade, Cortical Cataract Grade and Posterior Cataract Grade will be summarised by visit, by eye, by period as well as overall. Shift from baseline will also be evaluated.

The categories for Lens Opacity Grades are defined as Category 1, 2, 3 and 4. Category 1 includes values 1, 1.0 and 0.x. Category 2 includes values 2, 2.0 and 1.x. Category 3 includes values 3, 3.0 and 2.x. Category 4 includes values 4, 4.0, 3.x and any values above 4.

The categories for the shift from baseline are defined as follows:

- No change in category
- Decrease in category
- Category 1 at Baseline to Category 2, 3 or 4
- Category 2 at Baseline to Category 3 or 4
- Category 3 at Baseline to Category 4

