11.10 Full Ophthalmic Examination

A full ophthalmic examination will be performed for both eyes at the times indicated in [Table 1](#).

Each ophthalmic examination will include IOP, slit lamp examination, lens opacity grading, and dilated ophthalmoscopy. The same slit lamp machine and lighting conditions should be used across study visits for any given subject.

In addition to the parameters listed above, subjects will be carefully examined for the presence of intraocular inflammation after vector administration. Cataract can also develop as a result of the vitrectomy procedure and can potentially affect VA. Pre-operative grading of lens opacity and colour should therefore be documented by the established clinical LOCS III. A recent study has shown that cataract surgery is effective in subjects with CHM and without any specific risks ([Edwards, Jolly et al. 2016](#)). Subjects who develop cataracts may undergo cataract surgery if deemed clinically necessary. If cataract surgery is performed, it should be carried out at least 4 weeks before Month 12 (Visit 9) for the respective eye.

11.11 7-Field Colour Fundus Photography

Seven-field colour fundus photography will be performed for both eyes at the times indicated in [Table 1](#).

Fundus photography will be performed by certified technicians following pupil dilation. Stereo photos should be performed for fields 1, 2 and 3. All fundus photographs will be sent by the sites to the CRC for review; the CRC will enter the data into the EDC system. For complete technical specifications for fundus photography, refer to the Study Operations Manual.

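### Lens-opacity grades are rounded up into categories and only category crossings are tabulated, so a 0.1-unit rise can show as a shift while a 0.9-unit rise shows as none

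*SAP*

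**What the plan says.** Protocol 6.2 lists lens opacity grading among the safety measures. Protocol 11.10 gives the reason: "Cataract can also develop as a result of the vitrectomy procedure and can potentially affect VA". The same section then names the grading scale to be used: "Pre-operative grading of lens opacity and colour should therefore be documented by the established clinical LOCS III". Protocol 13.6.2 sets the analysis without cut-points or a minimum change: "Lens opacity categories and shifts from baseline will be summarised by eye, period and visit".

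The cut-points are set in SAP 4.17.4. The two lower bands are given as "Category 1 includes values 1, 1.0 and 0.x. Category 2 includes values 2, 2.0 and 1.x". The two upper bands follow the same pattern, but the last one is left open at the top: "Category 3 includes values 3, 3.0 and 2.x. Category 4 includes values 4, 4.0, 3.x and any values above 4". The counts are planned for each visit, eye and period, and overall, and they cover all four scales ("The number and percentage of subjects within each category of Nuclear Opalescence Grade, Nuclear Colour Grade, Cortical Cataract Grade and Posterior Cataract Grade will be" is how that sentence opens). The shift table has five rows: "No change in category", a decrease, and one upward row for each of baseline Categories 1, 2 and 3, such as "Category 1 at Baseline to Category 2, 3 or 4". No upward row has a minimum size.

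No numeric summary of the grade or of its change is planned. By contrast, SAP 4.17.2 summarises both the value and the change from baseline for intraocular pressure, which belongs to the same ophthalmic examination.

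**The concern.** The SAP's own notation (0.x, 1.x and so on) shows that decimal grades are expected. Rounding them up and then counting only crossings makes the meaning of a row depend on where the eye started. An eye just below a cut-point needs one tenth of a unit to enter an upward row; an eye just above one can gain nine tenths and be shown as unchanged. The decrease row has the same defect: 1.1 to 1.0 is a decrease, while 2.0 to 1.1 is not.

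Both eyes undergo vitrectomy, Protocol 5.4 names cataract as a complication of it, and loss of visual acuity is an identified risk of the product. The lens table is one place a reader will look when asking whether a letter loss could come from the lens. In a study with no formal comparison, the descriptive tables are the result, so what each row means matters.

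**Working it through.** **Inputs.** The category boundaries and shift rows are from SAP 4.17.4. The documents give no figure to reproduce for this point. Two things are assumed: grades recorded in steps of 0.1, suggested by the SAP's notation, and a lowest grade of 0.1.

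**Rule as a formula.** Category(g) = min(4, max(1, g rounded up to the next whole number)). Since 1.0 is named in Category 1, 1.x starts at 1.1; likewise at the other cut-points.

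**Single cases.**

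| Baseline to visit | Change | Categories | Row |
|---|---|---|---|
| 1.0 to 1.1 | +0.1 | 1 to 2 | upward shift |
| 1.1 to 2.0 | +0.9 | 2 to 2 | no change |
| 2.0 to 2.1 | +0.1 | 2 to 3 | upward shift |
| 2.1 to 3.0 | +0.9 | 3 to 3 | no change |
| 3.0 to 3.1 | +0.1 | 3 to 4 | upward shift |
| 3.1 to 4.0 | +0.9 | 4 to 4 | no change |

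Over grades 0.1 to 4.0, the smallest rise shown as an upward shift is 0.1 and the largest shown as no change is 0.9. Category 4 has no upper limit, so above 4.0 the hidden rise can be larger: 3.1 to 5.0 (+1.9) is also no change.

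**Share of baselines.** There are 30 baselines from 0.1 to 3.0. Within each band of ten, a rise of k tenths (k up to 10) crosses the cut-point from the top k values. The share is therefore 3k/30:

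- rise 0.1: 3/30 = 10%
- rise 0.5: 15/30 = 50%
- rise 0.9: 27/30 = 90%
- rise 1.0: 30/30 = 100%

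**Grading noise, illustration only.** Suppose there is no true change and the visit-minus-baseline difference is normal with mean 0 and an assumed SD of 0.2 to 0.5, recorded to 0.1. For baseline b below cut-point U, P(upward) = 1 − Φ((U − b + 0.05)/SD). Averaged over evenly spread baselines:

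| Baselines | SD 0.2 | SD 0.5 |
|---|---|---|
| 0.1 to 3.0 | 7.9% up | 19.5% up |
| 0.1 to 1.0 | 7.9% up | 19.5% up |
| 0.1 to 0.5 | 0.1% up | 7.5% up |

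Downward crossing is about 5% to 13% for the first set and 0% for the other two, because Category 1 eyes cannot move down. If baselines sat at exactly 1.0, the upward share would be 1 − Φ(0.05/0.2) = 40% to 1 − Φ(0.05/0.5) = 46%. The result is driven by the assumed baselines.

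**The case against.** The best defence is that the SAP delivers what Protocol 13.6.2 asks for, that any categorisation has edge effects, and that cataract is also assessed elsewhere. SAP 4.17.3 tabulates a slit-lamp shift for the lens by clinical significance. SAP 4.17.10 tabulates adverse events by term, severity and relatedness. SAP 4.17.1 tabulates losses of at least 5, 10 and 15 letters. This stands in part: it rules out any inference that lens progression would vanish from the study report. It does not restore the lost information, since none of these uses the recorded grade.

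Three stronger readings are tempting and are not supported.

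- A reader might take 8% to 20% as the expected rate of false progression. That range needs an assumed SD and evenly spread baselines. Clinically significant cataract is an exclusion, so low baselines are plausible, and with baselines of 0.1 to 0.5 the range falls to 0.1% to 7.5%.
- A reader might infer that differences between sites in cataract rates would partly reflect recording style. Lens grades are not tabulated by site; SAP 4.7 limits site summaries to demographics, baseline characteristics and BCVA. Nor do the documents define a cataract rate from this table. That some graders use whole numbers is only an inference from the SAP listing both 1 and 1.0, which may be no more than data formats.
- A reader might conclude that worsening should be defined as a rise of at least 1.0 unit. No document supports that threshold, and it misses every 0.5- and 0.9-unit rise recorded in decimals. It would also widen any gap between recording styles. For a true rise of 0.5 over the 30 baselines it flags 0% of decimal grades. It flags 15/30 = 50% of grades recorded as whole numbers, because each rounded grade then steps up by one in half the cases.

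**Conclusion.** The point holds for the lens-grade table in SAP 4.17.4. By its own rule, the table can show a 0.1-unit rise as an upward shift and a 0.9-unit rise as no change, and no other planned output shows the recorded grade. The 10%, 50% and 90% shares follow from the rule and the 0.1-step grid alone. How many eyes would be affected cannot be computed from the documents; across the evenly spread baselines tried above, spurious upward shifts run from about 0.1% to 20%.

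The SAP speaks of shifts, not worsening, and no test depends on the table. This is a low-cost improvement to one descriptive safety display. It does not make the planned table invalid.

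**What to change.** In SAP 4.17.4, for nuclear opalescence, nuclear colour, cortical and posterior cataract grades, add descriptive statistics with 95% CI for the observed grade and for the change from baseline in the recorded grade, by visit, eye and period. The t-based interval of SAP 4.2 applies, and Protocol 13.4 already foresees this form of summary for continuous variables. Keep the category counts and shift rows as the descriptive display that Protocol 13.6.2 requires. Do not substitute a fixed unit threshold for worsening.

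The cost is a sentence or two in the SAP and one extra table. The grades are already collected, so no new assessment or visit is needed.
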